6.7. Definition of End of Study

The end of study is the date of the last follow up (videoconference) of the last participant.

7. INTERVENTIONS

A five-day intervention with tDCS (bi-hemispheric vs. sham) combined with speech fluency training will be carried out.

tDCS: Participants will receive five daily sessions of real tDCS combined with speech training, or sham stimulation combined with speech training, according to which arm of the trial they are randomly assigned. Stimulation will be applied for no more than 20 minutes per session. Stimulation will be carried out in accordance with the protocol for the Central University Research Ethics Committee for use in healthy volunteers. Our study will be carried out in accordance with procedures outlined in the SOP and will not exceed the recommendations of the approved protocol. Please see section 7.6 for addition information regarding tDCS procedure.

Speech fluency training: Participants will complete speech tasks whilst speaking to an external beat (metronome-timed speech). Different tasks will be used during the 20 minutes of stimulation and repeated for a further 20 minutes once the stimulation has ended. The order of tasks will be randomised across the five days of speech training. The duration of each training session will be one hour, and participants will receive concurrent tDCS for 20 minutes at the start of the fluency training. Participants will also complete brief speech tasks before and after the training.

8. SAFETY REPORTING

8.1. Definition of Serious Adverse Events

A serious adverse event is any untoward medical occurrence that:

- results in death
- is life-threatening
- requires inpatient hospitalisation or prolongation of existing hospitalisation
- results in persistent or significant disability/incapacity
- consists of a congenital anomaly or birth defect.

Other 'important medical events' may also be considered serious if they jeopardise the participant or require an intervention to prevent one of the above consequences.

NOTE: The term "life-threatening" in the definition of "serious" refers to an event in which the participant was at risk of death at the time of the event; it does not refer to an event which hypothetically might have caused death if it were more severe.

8.2. Reporting Procedures for Serious Adverse Events

A serious adverse event (SAE) occurring to a participant will be reported to the Medical Sciences IDREC that gave a favourable opinion of the study where in the opinion of the Chief Investigator the event was 'related' (resulted from administration of any of the research procedures) and 'unexpected' in relation to those procedures. In addition, these events will be reported to the relevant safety officers at OHBA and the Department of Experimental Psychology. Reports of related and unexpected SAEs should be submitted within 15 working days of the Chief Investigator becoming aware of the event.

9. STATISTICS AND ANALYSIS

9.1. Description of Statistical Methods

Behavioural data measuring the primary outcome (speech function) will be acquired before, during and after brain stimulation using audio and video recordings. Measures of speech fluency (e.g. Stuttering Severity Instrument score, % disfluency) will be taken from these recordings and will be subjected to standard statistical analyses using software such as SPSS. Mixed between- and within-subject designs will be used to compare changes in performance (baseline subtracted) on speech measures between the two groups of participants (tDCS vs. sham). The investigator team have prior experience in statistical analysis of similar behavioural data.

Brain imaging data (MRI) will be analysed using the FMRIB Software Library (FSL) which involve standard approaches for the analysis of functional imaging data. We will also be using novel approaches that allow us to explore functional connectivity, such as probabilistic Independent Component Analysis. The investigator team has substantial with MRI analysis using FSL and SPM.

Vocal Tract Images will be analysed using custom tools implemented in MATLAB.

TMS data will be analysed using custom tools and software to compare measures of cortical excitability within participants between hemispheres, and across time points, and between groups at the baseline timepoint.

While the study is ongoing, we will be able to compare brain and vocal tract imaging, and TMS data in PWS vs controls once we have data from the baseline timepoint. Unblinding is not required for these baseline analyses.

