1. SYNOPSIS

Study Title	Investigating non-invasive brain stimulation to enhance fluency in people who stutter
Internal ref. no. / short title	INSTEP Trial
Study Design	Double-blind randomised controlled trial. Active treatment: bi-hemispheric tDCS, Control: Sham tDCS. Minimisation randomisation.
Study Participants	Healthy adult males with developmental stuttering and healthy male controls with no speech disorders
Planned Sample Size	70 (40 participants with developmental stuttering, 30 control participants)
Planned Study Period	1 st November 2017 – 30th April 2020
	Outcome Measures
Primary	Change from baseline (i.e. baseline subtracted) in a clinical measure of stuttering severity (SSI-4), post training (1 week, 6 weeks, and 3 months after training).
Secondary	Change from baseline (i.e. baseline subtracted) in: (i) % disfluent syllables produced during conversation; (ii) % disfluent syllables produced during reading post training (1 week, 6 weeks, and 3 months after training). (iii) total score on an attitudinal measure (OASES), post training (6 weeks, and 3 months after training).
Other Pre-specified	Change from baseline (i.e. baseline subtracted) in: (i) total score on the Premonitory Awareness in Stuttering Scale; (ii) total score on the Beck Anxiety Inventory; (iii) subjective and objective ratings of stuttering severity and naturalness, post training (1 week, 6 weeks, and 3 months after training). Changes from baseline (i.e. baseline subtracted) % disfluent syllables produced during (i) conversation and (ii) reading, during the 5-day training (immediately post intervention days 1 to 5; immediately pre-intervention days 2 to 5).
	Exploratory (non-behavioural) measures
Other	We will use MRI and TMS, to evaluate neural structure, function, and excitability in people who stutter and in healthy controls. Using MRI, we will also obtain images of the vocal tract during speech. These measurements will be obtained just before training begins and 1 week after the end of the training in people who stutter and once only in healthy controls.

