3. BACKGROUND AND RATIONALE

Developmental stuttering is a disorder affecting the fluency of speech, characterized by repetitions or prolongations of sounds and frequent hesitations or pauses. It affects 5% of children and persists to adulthood in about 1%. Changing the way speech is produced in adults who stutter is a particular challenge for speech and language therapy and there is a need for novel interventions, therefore. One such intervention involves the application of transcranial direct current stimulation (tDCS) alongside speech therapy. tDCS influences brain activity by modulating neuronal plasticity through the application of weak electrical currents across the brain. Pairing tDCS with speech therapy has potential for producing larger or longer lasting effects and reducing time spent in therapy. In a previous study, we showed that a five-day training regime of anodal tDCS combined with temporary fluency enhancers led to improvements in speech fluency in PWS that were sustained for five weeks post intervention.

The first aim of our study is to replicate our previous finding using a slightly different form of tDCS combined with speech fluency training to improve outcomes in people who stutter (PWS). We will use metronome-timed speech to temporarily induce fluency during the training. PWS will have this training for 40 minutes a day while receiving anodal tDCS over the left frontal cortex and cathodal tDCS over the right frontal cortex for five consecutive days (1mA for 20 mins at the start of the intervention on each day) in a double-blind randomized controlled trial. Outcomes

will be measured in terms of changes to stuttering severity, dysfluency rates for reading and conversation, naturalness ratings, and attitudes to stuttering.

The second aim of our study is to understand how changes in the interactions between sensory and motor regions of the brain relate to changes in speech fluency in PWS. We will use MRI to measure brain structure and function. We will also image the vocal tract during speech production. Transcranial magnetic stimulation (TMS) will evaluate changes in excitability of the motor system underlying speech production. These studies are exploratory measures of the intervention in PWS.

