9.3. Analysis of Outcome Measures

Only data from participants who have not withdrawn consent will be included in final analyses. If participants drop out, we will attempt to replace their participation.

We will compare measures of speech function based on standardized tests and measures of speech fluency from speech samples. The primary outcome is defined as change in SSI-4 score (baseline subtracted), and the secondary outcomes are change in % disfluency and OASES score.

Differences between sham and tDCS intervention in brain imaging measurements will be evaluated using standardized analysis tools in the FMRIB Software Library. In functional MRI our outcome measures are the intensity and size of activation clusters based on the recorded blood-oxygenation-level-dependent signal (BOLD) that are involved in the tasks we ask participants to complete. Structural image analysis will be employed to measure white matter diffusion and grey matter morphometric differences in areas identified as abnormal in previous studies of stuttering.

Vocal tract imaging data will be analysed using custom tools to calculate the range of positions in tongue blade movement, lip protrusion, and laryngeal lowering during speech production. We predict that spatiotemporal variability in these movements will be greater in PWS compared with controls and reduce in those with measureable improvements in fluency following speech training.

The motor excitability and measures of cortical connectivity obtained using TMS and MEPs will be compared in PWS and Controls and at baseline relative to week 1 to examine for correlates of improved speech fluency in PWS.

We will compare differences in brain and vocal tract imaging data in PWS and controls. Only data from the baseline time point will be used.

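### No tDCS-versus-sham comparison of change is stated for the TMS and vocal tract measures, although both arms are measured before and after training

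*Protocol*

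**What the plan says.** - **Purpose.** Protocol Section 3 introduces MRI, vocal tract imaging and TMS under the second aim and closes: "These studies are exploratory measures of the intervention in PWS".
- **Timing.** The Synopsis says of these measures: "These measurements will be obtained just before training begins and 1 week after the end of the training in people who stutter". Controls are measured once. Appendix B marks TMS and vocal tract MRI at Visit 1 and Visit 7.
- **TMS analysis.** Section 9.1 uses custom software "to compare measures of cortical excitability within participants between hemispheres, and across time points, and between groups at the baseline timepoint". Section 9.3 says the TMS measures "will be compared in PWS and Controls and at baseline relative to week 1 to examine for correlates of improved speech fluency in PWS".
- **Vocal tract analysis.** Section 9.1 names MATLAB tools. Section 9.3 plans a comparison of stutterers with controls on baseline data only. Its one post-training statement is a prediction that movement variability will "reduce in those with measureable improvements in fluency following speech training".
- **Where the randomised contrast is written.** For behaviour, Section 9.1 uses mixed designs "to compare changes in performance (baseline subtracted) on speech measures between the two groups of participants (tDCS vs. sham". For brain imaging, Section 9.3 states: "Differences between sham and tDCS intervention in brain imaging measurements will be evaluated using standardized analysis tools in the FMRIB Software Library".
- **SAP.** It covers the behavioural outcomes and does not mention TMS or vocal tract imaging.

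**The concern.** Protocol Section 6.3 gives both arms identical speech training; only the stimulation differs. A change in excitability or vocal tract movement between Visit 1 and Visit 7 can therefore come from tDCS, from five days of metronome-timed training, from repeat testing or from the passage of time. Controls have no second measurement, so they cannot show what retest and time do alone. The sham arm is the only comparator that can separate tDCS from the rest, and the analysis text does not use it for these measures.

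Correlating the change with fluency gain does not close the gap. Fluency may improve in both arms through training, so a correlation across all participants who stutter can arise without any tDCS effect.

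At stake is whether these exploratory data can say anything about stimulation as such. If the contrast is left unstated, it is also open which comparison will be chosen once the data are unblinded.

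**Working it through.** **1. Which contrasts are stated**

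| Measure | Across time in stutterers | Stutterers vs controls at baseline | tDCS vs sham on change |
|---|---|---|---|
| Speech measures | yes (9.1, SAP) | not applicable | yes (9.1, SAP) |
| Brain imaging (FSL) | through the arm contrast (9.3) | yes (9.1, 9.3) | sham and tDCS differences stated (9.3) |
| TMS | yes (9.1, 9.3) | yes (9.1, 9.3) | not stated |
| Vocal tract imaging | prediction only (9.3) | yes (9.1, 9.3) | not stated |

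The brain-imaging sentence does not cover the last two rows. It names brain measurements and FSL, whereas Section 9.1 assigns vocal tract images to MATLAB tools and TMS to custom software.

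**2. What each comparison estimates**

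Let C be the mean change in the sham arm (training, retest and time), and T the extra mean change in the tDCS arm, including any interaction of stimulation with training.

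- Change in the tDCS arm: C + T.
- Change in the sham arm: C.
- Both arms pooled, 20 + 20: [(C + T) + C] / 2 = C + T/2.
- tDCS minus sham: (C + T) − C = T.

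Only the last isolates T. If T = 0, the pooled change equals C, which need not be zero.

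**3. The plan's own sample-size figure**

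Inputs from Section 9.2: effect size 0.9, 80% power, 5% false positive rate, 20 per group. Sidedness is not stated; two-sided is assumed.

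- Normal approximation: n = 2(1.960 + 0.842)² / 0.9² = 19.4, rounded up to 20 per group. One-sided would give 16.
- Power at 20 per group: Φ(0.9·√(20/2) − 1.960) = Φ(0.886) = 81.2%. The exact t test gives 79.2%.

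The stated figure reproduces.

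**4. What the missing contrast could detect**

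For a two-sided 5% t test of change scores, 20 versus 20, the difference detectable at 80% power is 0.91 SD of the change. This is essentially the 0.9 already in Section 9.2.

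**5. Loss of precision**

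With σ the SD of change in each arm:

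- Standard error of the pooled mean change in 40: σ/√40 = 0.158σ.
- Standard error of the difference between arms: σ·√(1/20 + 1/20) = 0.316σ.

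The between-arm contrast has twice the standard error, but it is the one that estimates T.

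**The case against.** The best defence is that the analysis matches its aim. Section 3 frames the second aim as relating brain changes to changes in fluency, and Section 9.3 looks for correlates of improved fluency. The intervention is tDCS combined with training, and no section promises to isolate a tDCS effect on excitability. The Synopsis lists these measures as exploratory.

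Much of this stands. The correlational use is legitimate, and the primary and secondary comparisons do not depend on these data. But brain imaging is equally exploratory and does get a sham-versus-tDCS comparison, so exploratory status does not explain the omission.

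Four stronger readings are tempting and are not supported:

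- *The randomised comparison of TMS has been restricted to baseline.* In Section 9.1 the groups at baseline are most likely stutterers and controls. Controls are measured once, and the closing paragraph of 9.1 describes that comparison as needing no unblinding. The protocol is silent on tDCS versus sham for TMS; it does not confine that contrast to baseline.
- *The trial cannot attribute a change to tDCS.* The data to be collected would support the contrast. Only the analysis as written does not.
- *The vocal tract analysis is limited to participants who improved.* That sentence is a prediction and does not define an analysis set.
- *The before-after test has a high false positive rate.* With an assumed common change of 0.2, 0.3 or 0.5 SD of change and no tDCS effect, a pooled paired t test in 40 would be significant in 24%, 46% or 87% of trials. That is power to detect a real change, not an error rate, and it should not be set against 5%. The shifts are assumptions, and the protocol does not specify a pooled paired test.

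Nor do the documents say that a before-after change would be reported as a tDCS mechanism.

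**Conclusion.** The concern holds in limited form. For TMS and vocal tract measures, the protocol states no comparison of change between the randomised arms, and the SAP does not supply one. Followed as written, the before-after results describe change in people who stutter and cannot distinguish stimulation from training, retest or time.

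The consequence is confined to exploratory measures. It is worth correcting before unblinding because the data and the sham control are already in the design.

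The 0.91 SD figure assumes a two-sided 5% t test, equal SD of change in the two arms, and usable data at both visits in all 20 per arm; fewer completers would raise it. The documents give no TMS or vocal tract means or SDs, so it cannot be put in the units of any measure. An effect smaller than this could easily be missed, so a non-significant difference would not show that tDCS has no effect.

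**What to change.** In Sections 9.1 and 9.3, add that the Visit 7 minus Visit 1 change in each TMS measure and each vocal tract measure will be compared between tDCS and sham in all participants who stutter, as an exploratory analysis. Reporting the difference with a confidence interval would make the limited precision visible.

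Keep the across-time, hemisphere and fluency-correlate analyses, and say that they describe change and are not evidence of a tDCS effect. In Section 9.1, also say that the groups compared at baseline are stutterers and controls, if that is what is meant.

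The cost is a few sentences and one extra comparison per measure, with twice the standard error of a pooled before-after estimate. No new participants, visits or data are needed.

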9.2. The Number of Participants

We plan to recruit 40 PWS and up to 30 controls. The sample size was determined based on previous cross-sectional studies in stuttering, including our own. A sample size of 20 participants in each group is higher than most previous behavioural and functional imaging studies in PWS. This should ensure sufficient sensitivity to detect differences in behaviour, brain structure and function. It should also allow us to determine the relationship between the experimental variables and other measures such as stuttering severity and duration of stuttering. A sample size of 20 for each group should detect a group difference with an effect size of 0.9 at 80% power and 5% false positive rate. For the tDCS study across 5 days, we will compare two groups of 20 PWS. In our previous study, with sample sizes of 15 in each group, effect sizes of 0.93 and 0.50 were obtained for the reduction in the SSI at 1 week and 6 weeks post intervention.

9.3. Analysis of Outcome Measures

Only data from participants who have not withdrawn consent will be included in final analyses. If participants drop out, we will attempt to replace their participation.

We will compare measures of speech function based on standardized tests and measures of speech fluency from speech samples. The primary outcome is defined as change in SSI-4 score (baseline subtracted), and the secondary outcomes are change in % disfluency and OASES score.

Differences between sham and tDCS intervention in brain imaging measurements will be evaluated using standardized analysis tools in the FMRIB Software Library. In functional MRI our outcome measures are the intensity and size of activation clusters based on the recorded blood-oxygenation-level-dependent signal (BOLD) that are involved in the tasks we ask participants to complete. Structural image analysis will be employed to measure white matter diffusion and grey matter morphometric differences in areas identified as abnormal in previous studies of stuttering.

Vocal tract imaging data will be analysed using custom tools to calculate the range of positions in tongue blade movement, lip protrusion, and laryngeal lowering during speech production. We predict that spatiotemporal variability in these movements will be greater in PWS compared with controls and reduce in those with measureable improvements in fluency following speech training.

The motor excitability and measures of cortical connectivity obtained using TMS and MEPs will be compared in PWS and Controls and at baseline relative to week 1 to examine for correlates of improved speech fluency in PWS.

We will compare differences in brain and vocal tract imaging data in PWS and controls. Only data from the baseline time point will be used.

10. DATA MANAGEMENT

10.1. Access to Data

Direct access will be granted to authorised representatives from the University of Oxford and any host institution for monitoring and/or audit of the study to ensure compliance with regulations. We also expect our results will be published in a scientific journal and that anonymised data will be uploaded to recognised open data repositories at the end of the study (such as openfMRI) at

the end of the study. Video recordings will be made of participants speaking and this is the basis of our primary outcome measure. The video/audio data collected in this study will not be shared on data repositories, as it cannot be sufficiently anonymised. We would not normally give feedback about results to individual participants.

10.2. Data Recording and Record Keeping

All study data will be kept strictly confidential. A unique study specific number i.e. a code will identify the participants in databases created for the study, and identifying information associated with this code will be stored in a locked filing cabinet in the Department of Experimental Psychology. Names and any other identifying detail will NOT be included in any study data electronic file.

Brain imaging and stimulation data will also be anonymised using the study specific code and will be stored on password-protected computers in the Department of Experimental Psychology or OHBA respectively and backed up on hard disks. Video/audio recordings of the participant will also be associated with this code and backed up on Departmental servers. Data will be stored for 5 years following the final publication related to the study.

Students and collaborators may be given access to fully anonymised data and the video recordings under the supervision of the named investigators and with approval of the Chief Investigator. Some peer-reviewed journals require submission of anonymised data and anonymised data may also be uploaded to other data sharing initiatives. Access may be given to responsible members of the University of Oxford for the purposes of monitoring or audit.

